**3. \* Choose all types of recruitment materials that may be used and upload them below:**

- E-mail invitations
- Phone Solicitation scripts (i.e. cold calls or random-digit-dialing)
- Flyers, Mailed Letters or Newspaper/TV/Radio Ads**
- TelegRAM announcements
- Website text
- Study-specific web sites (provide the design and text)
- Social Media
- EPIC MyChart Patient Portal research study descriptions
- Psychology Research Participant Pool (SONA) study descriptions
- Scripts for announcements made to groups
- Other recruitment document
- No recruitment materials

**4. \* Describe the study procedures/methods for identifying and recruiting participants. Address all of the following three aspects of recruitment in your response.****1. Identification of potentially eligible participants or secondary data/specimens of interest.**

- What database(s) will be queried to identify secondary data/specimens

- How VCU Informatics or VCU IRDS will be used for cohort identification (when applicable, see help text)
- How potential participants' contact information will be obtained

**2. Recruitment procedures to invite participation in the study (when applicable):**

- How each of the written or verbal recruitment materials and reminders (selected above) will be used
- Who will contact, approach, or respond to potential participants
- Locations where recruitment procedures will take place
- The timing and frequency of recruitment attempts

**3. Eligibility screening prior to consent and how those activities will be carried out (when applicable)**

**See the help text for additional guidance.**

Students will be recruited through their schools through (a) a flyer advertising an informational meeting for students and parents with information about the study; (b) a letter to students and parents sent by the school, and (c) regularly scheduled Individualized Education Plan (IEP) meetings at which parents and students attend. Information about the study will be provided to students and to their families.

Potential participants will submit an application that contains their contact information. (See Application for Participation located in the recruitment materials sections).

Recruitment activities will be held from January through May of years 1 and 2. Recruitment may occur in year 3 if there is significant attrition of participants. Once all participants are enrolled and identified, we will assign a number to each enrolled participant and complete randomization using a random numbers generator on a computer. The individual completing randomization will not know the identity or group to which individuals are assigned.

Recruitment procedures will be completed as follows:

1. Each school district representative who participates on the coordinating team will schedule an informational meeting in their school division for potential participants from their schools.
2. Applications and flyers announcing informational meetings will be sent to all school district representatives to share with potential participants in January of years 1, 2, and potentially 3.
3. Informational meetings will be held at the times and in the locations identified by the school district representatives.
4. If potential participants or their family members are unable to attend the informational meetings, VCU staff will meet with them at a time and location of their choosing.
5. At each informational meeting, potential participants and their family members will receive an application with instructions on how to apply, when and where to deliver completed applications.
6. VCU staff will answer any questions from potential participants regarding the research.
7. Upon receipt of the application, VCU staff will coordinate with the screening team to schedule screening interviews in a private location that is convenient to the potential participant and their family members.

**Screening Procedures:**

There will be two screening meetings held for all potential participants. The first meeting, the research screening meeting, will be for the purposes of completing consent and assent documentation, completing the subject eligibility checklist and reviewing research procedures with potential participants and their family members. This first research screening meeting will include the researcher or their designee, the potential participant, and their family members or guardians only. It will be held at a location of the participant and their family's choosing that is private with a door that is able to be closed to further maintain privacy. If the potential participant and their guardians agree to participate by signing the consent and assent documents, a second "Project SEARCH Screening meeting will be scheduled.

The Project SEARCH Screening meeting will be held in private locations convenient to the potential participant and their family members. These are most often held at the potential participant's school in a closed room, such as a guidance counselor's meeting room. The following people from the Project SEARCH team participate:

1. A VCU representative trained in the research protocol and completing consent/assent discussions
2. A Project SEARCH teacher or job coach
3. A Department of Aging and Rehabilitative Services Counselor
4. The Coordinating team member from the school division where the potential participant receives their education.
4. The potential participant
5. The potential participant's family members
6. The potential participant's current teacher (if acceptable to the potential participant)

During this meeting, the team mentioned above will complete the Student Screening and Interview Rubric.

In some cases, the potential participant is unable to verbally participate or has difficulty answering questions in the screening interview. When that is the case, the student will be asked if the VCU Representative and/or the Project SEARCH teacher or job coach can observe the potential participant in their classroom at their home school. The purpose of this observation is to be able to answer questions through observation that the person or their team could not answer in the interview.

(See the attached Student Screening Interview and Rubric in the Supporting Documents)

5. \* Does this study have a separate protocol document (i.e. a multisite or sponsor's protocol) that contains a detailed description of the study's methodology?

Yes

No

6. \* Since a separate protocol document is not uploaded, describe the proposed research using language understandable to those IRB committee members whose expertise is not scientific. The description must include:

1. A statement explaining the study design
2. A detailed description of all the procedures that will be followed to carry out the study, preferably in sequential order, and in sufficient detail that the study's methods could be replicated
3. The schedule and frequency of when and how procedures will be conducted (e.g. in person, online, phone, paper, etc.)
4. A description of all research measures/tests/interventions that will be used, including analyses/tests conducted on specimens/biological samples (if applicable)

**See the help text for additional guidance**

This is a randomized, wait-list controlled study of the efficacy of the Project Search plus ASD Supports Model (PS+ASD) in 32 adolescents and young adults aged 18 to 22 with ASD. Approximately 32 subjects will be enrolled and randomized in a 1:1 ratio to treatment or wait-list control. A sufficient number of potential subjects will be screened to achieve this number of enrolled subjects.

The six dependent variables in question are the primary endpoint employment rate (upon completion and at 12 months and 18 months post-enrollment) and the secondary endpoints hourly wages, hours/week, Social Responsiveness Scale total score, Behavior Assessment System for Children 3rd Ed. Anxiety and Depression t-score and the Quality of Life Questionnaire percentile score at baseline (Baseline), 12 months post enrollment (12 months), and 18 months post-enrollment (18 months). The efficacy of the intervention will be analyzed by comparing the differences in these six variables between the treatment group and the control group.

The study will take place at Fort Eustis in collaboration with the local school division, Newport News, Hampton City, York County, Williamsburg James City County Public Schools, and the New Horizons Regional Education Center where most military dependents receive their education. The participating public schools will identify a teacher consultant and instructional assistant to staff the project. Additionally, we will collaborate with a variety of department at Fort Eustis Military base where the project will be housed. We will also collaborate with the Virginia Department of Aging and Vocational Rehabilitation Services (DARS) as well as Business Connections, VCU's Community Rehabilitation Provider for job coaching services. At baseline, we will collect demographic and descriptive data to assist us in identifying and describing the prior experiences and current situation for the participants in the study. The demographic variables collected will be age, gender, and race. We will also collect information regarding the military dependent with ASD's parents' military status including identification of the currently serving military parent(s), living situation, school division where served, and the current location of assignment of first and/or second military parent. In addition, we will collect total household income in ranges to assess the variability of employment outcomes based upon yearly total household income. We will collect diagnostic information regarding the participant including medical diagnosis, primary educational disability category, secondary educational disability category and intelligence quotient. Finally, we will collect information regarding the participant's work, internship, and educational experience. In addition to these variables, we will also complete the Support Intensity Scale (SIS). The SIS is an interview based assessment tool that identifies the type, amount, and frequency of support required by individuals with significant disabilities, including persons with autism, to perform 57 life activities. An additional 28 items address behavioral and medical areas. The assessment is completed through an interview with the individual, as well as family, school, and community members with in-depth knowledge of the individual. The assessment generates a composite scale score and individual scale scores in the areas of home living, community living, lifelong learning, employment, health and safety, and social areas. Completion of the SIS will allow us to describe the impact that the military dependents experiences as a result of their ASD. It is also a clinical tool that will allow us to ensure that all participants get the appropriate level of support to achieve their desired outcome. All collected paper data will be stored in locked file cabinets. All electronic data will be de-identified and stored in encrypted files on encrypted, password protected computers. All data collectors will be trained to complete all data collection to protect the confidentiality of the participants. In some cases where participants are not able to answer questions on the measures, parents or guardians may be asked to answer these questions. Because this will be determined on a case by case basis, parents and guardians will also be considered research participants for the purposes of consent.

Project SEARCH is an intensive 9-month job training program where youth with developmental disabilities in their last year of high school are embedded in a large community business such as a hospital, government complex, or banking center where they rotate through three 10-12 week internships within the business. Subjects will log approximately 720 hours of internship time learning marketable skills and 180 hours of business site classroom time learning social communication and adaptive behavior for a total of approximately 900 hours embedded in the business setting. In order to meet the unique needs of youth with ASD, [name], et al. enhanced the Project SEARCH model by adding autism supports to the original model. Those added supports were: 1) on-site, intensive, systematic instruction using the principles of applied behavior analysis, 2) on-site support and consultation from a behavior/autism specialist, and 3) intensive staff training in ASD and the Project SEARCH Model. This resulted in PS+ASD. It is the impact of this intervention for military dependents with ASD we will assess through this project.

As a part of this study, we will collect the following educational records:

1. The Individualized Education Plan for each student.
2. The student's attendance record to assess the student's fitness to participate in the study
3. The student's transcript to insure eligibility for the study
4. The student's prior work/study history for demographic information

5. Any prior career assessment information to assist in understanding the student's job training desires and needs.

Participation in this study will not be considered a part of the credits a student needs to complete graduation requirements.

We have submitted and received approval for our research protocol from the Human Research Protection Office of the DoD.

Prior to enrollment, each potential participant will complete an application for participation and will also complete a screening interview. Neither the application nor the screening interview will be used to collect data for research purposes. Instead, these activities are standard parts of the Project SEARCH program. The screening interview serves three purposes. First, it allows the team to describe Project SEARCH to the potential participant and ask any questions they may have. Second, it allows the research team to review the consent and assent documents and give participants an opportunity to ask questions about the research procedures. Third, it gives the Project SEARCH team the opportunity to interview the potential participant to learn more about their future career goals and to confirm their support needs. All screening meetings are held in private locations convenient to the potential participant and their family members. These are most often held at the potential participant's school in a closed room, such as a guidance counselor's meeting room. The following people from the Project SEARCH team participate:

1. A VCU representative trained in the research protocol and completing consent/assent discussions
2. A Project SEARCH teacher or job coach
3. A Department of Aging and Rehabilitative Services Counselor
4. The Coordinating team member from the school division where the potential participant receives their education.
4. The potential participant
5. The potential participant's family members
6. The potential participant's current teacher (if acceptable to the potential participant)

In some cases, the potential participant is unable to verbally participate or has difficulty answering questions in the screening interview. When that is the case, the student will be asked if the VCU Representative and/or the Project SEARCH teacher or job coach can observe the potential participant in their classroom at their home school. The purpose of this observation is to be able to answer questions through observation that the person or their team could not answer in the interview.

(See the attached Student Screening Interview and Rubric in the Supporting Documents)

7. \* The IRB only reviews research activities, so indicate for each of the study activities described in the question above or in the protocol which activities are:

- Being performed exclusively for research purposes (i.e. they would not otherwise be done apart from this study) VERSUS.
- Alterations of routine activities/procedures (e.g. the study is altering the timing, frequency, method, location, amount, etc.) VERSUS.
- Being done for other purposes and whose data/results will be used secondarily in the study (e.g. standard medical or psychological tests, routine education practices, quality improvement initiatives, etc.).

See the help text for additional guidance

The following procedures will be implemented for research purposes:

Screening  
Consent  
Randomization  
Assessment using:  
the Support Intensity Scale  
Interview using the baseline and 12 and 18 month follow-up interview  
Social Responsiveness Scale  
Behavior Assessment Scale for Children  
Quality of Life Questionnaire  
Collection of documents including the IEP, and Transition Plan.

The following procedures would take place in the same manner regardless of the research:

Potential Participant Application  
Project Search Team Interview Process  
9-month Project SEARCH Intervention  
Involvement by the Department of Aging and Rehabilitative Services  
Services provided by a job coach

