**4. \* List the study inclusion criteria:**

In order to be selected for inclusion in the sample pool, participants must meet the following criteria: (1) A diagnosis of Autism Spectrum Disorder; (2) between 18 - 22 years of age; (3) entering final year of school participation and is on track to receive a diploma or a certificate; (4) meets eligibility requirements for vocational rehabilitation; (5) possesses independent personal hygiene, eating and grooming skills; (5) able to pass drug screen and felony check and have immunizations up to date (These items will be seen by the community business only as required by them for interns to be present at their work site); and (6) desires and plans to work competitively in the community at the conclusion of the 9-month program, (7) Be a military dependent or military connected youth.

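### The completion employment rate that the study is powered on has no scheduled measurement, and the 12-month measure runs from an undated enrolment, so it may fall before the programme ends

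*Combined protocol and SAP*

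**What the plan says.** **Times for primary employment.** Study Procedures, item 6, names "the primary endpoint employment rate (upon completion and at 12 months and 18 months post-enrollment". The primary objective (Background, Rationale and Goals, item 3) names only 12 and 18 months after enrolment.

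**Collection.** Compensation, item 2, pays for baseline, 12 and 18 months and counts these as the three data collection points. Study Procedures, item 7, lists a baseline interview and a 12- and 18-month follow-up interview. Neither ties a contact to programme completion.

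**Power.** Study Population, item 3, uses pilot employment rates of 87% vs 6.7%, both described as rates at completion, with 16 treated and 22 controls. It claims power above 0.80 for a two-sided 5% Fisher exact test.

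**Calendar.** Study Procedures, item 4: "Recruitment activities will be held from January through May of years 1 and 2", and "Once all participants are enrolled and identified, we will assign a number to each enrolled participant and complete randomization". Item 6 adds: "Prior to enrollment, each potential participant will complete an application for participation and will also complete a screening interview". No enrolment date and no programme start month is given.

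**Place of the programme.** Participants are "entering final year of school participation and is on track to receive a diploma or a certificate". The programme is one "where youth with developmental disabilities in their last year of high school are embedded in a large community business", and on staffing: "The participating public schools will identify a teacher consultant and instructional assistant to staff the project". It lasts 9 months (Behavioral Intervention/Task Details, item 1). Competitive work is expected afterwards: the inclusion criteria require that the participant "desires and plans to work competitively in the community at the conclusion of the 9-month program".

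**The concern.** There are two separate problems.

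First, one of the three stated primary times has no visit behind it, and it is the one that the power statement depends on. For controls it is not even defined, because they do not complete anything during the comparison period.

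Second, the other two times count from enrolment. Enrolment comes before randomisation, and randomisation must come before the programme starts. A 9-month programme is over by month 12 only if it starts within 3 months of enrolment. Recruitment from January, for a programme that occupies the coming final school year, suggests a longer gap for many participants. Treated participants would then still be interns at month 12, while the plan expects the job to follow the internship. The comparison would be between interns and students, and it could miss a real effect that appears a few weeks or months later. Because the objective gives 12 and 18 months equal standing, a reader could take such a result as evidence against the programme.

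**Working it through.** **1. The plan's own figure.** Exact two-sided Fisher test at 5%, enumerating all tables, 87% vs 6.7%:

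- 16 vs 22: power 0.99996.
- 16 vs 16 (the 1:1 design of 32 in Study Procedures, item 6): power 0.9994.

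The claim of more than 0.80 is correct. The difficulty is the time to which the rates belong, not the arithmetic.

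**2. Stated times against scheduled collection.**

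| Stated primary time | Scheduled contact |
|---|---|
| Completion | none |
| 12 months after enrolment | yes |
| 18 months after enrolment | yes |

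**3. Where month 12 falls.** Completion, in months from enrolment = gap from enrolment to programme start + 9. This is at most 12 only if the gap is at most 3 months.

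Assumptions: enrolment on any of the 151 days from 1 January to 31 May; programme start as shown. Neither is stated in the documents, so a range is given.

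| Assumed start | Programme end | Days with month 12 before completion, January–May | Same, April–May only | Months since start at month 12 | Month 18, months after end |
|---|---|---|---|---|---|
| 1 August | 1 May | 120/151 (79%) | 30/61 (49%) | 5.0–10.0 | 2.0–7.0 |
| 15 August | 15 May | 134/151 (89%) | 44/61 (72%) | 4.6–9.5 | 1.5–6.5 |
| 1 September | 1 June | 151/151 (100%) | 61/61 (100%) | 4.0–8.9 | 1.0–6.0 |
| 15 September | 15 June | 151/151 (100%) | 61/61 (100%) | 3.6–8.5 | 0.5–5.5 |

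The April–May column follows by removing the 90 days of January–March, all of which put month 12 before completion: 120 − 90 = 30, 134 − 90 = 44, 151 − 90 = 61.

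**4. Other clocks.**

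- Month 0 = randomisation on 1 June, start 1 September: the gap is 3 months, so month 12 is the completion day (3 + 9 = 12). A later randomisation puts month 12 after completion.
- Month 0 = programme start: months 12 and 18 fall 12 − 9 = 3 and 18 − 9 = 9 months after completion.

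**5. Illustration of what is at stake.** The documents give no employment rate for interns before completion, so the treated rates below are assumptions. Control rate 6.7%, exact Fisher power:

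| Treated rate at month 12 (assumed) | 16 vs 22 | 16 vs 16 |
|---|---|---|
| 20% | 0.14 | 0.08 |
| 30% | 0.38 | 0.25 |
| 40% | 0.65 | 0.49 |
| 50% | 0.85 | 0.71 |

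Power of 0.80 needs a treated rate of about 47% with 16 vs 22, or about 56% with 16 vs 16.

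**The case against.** The strongest reply is that January–May dates recruitment activities, not enrolment. Applications and flyers go out only in January. Information meetings, an application, a consent and eligibility meeting, up to two weeks to decide and a second team screening follow. All of that pushes enrolment later, and item 6 places the application and screening interview before it. The order in which item 6 lists the times (completion, then 12, then 18 months) also suggests that the authors had in mind a clock starting near the programme. This stands. A reader might infer that the 12-month visit certainly falls inside the programme; the documents do not support that, because neither an enrolment date nor a start month is given. The 100% for a 1 September start is also a close call at the edge: a 31 May enrollee misses completion by one day.

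A second reply is that the 12- and 18-month interview script, which is listed but not reproduced, may ask about employment at completion in retrospect. That is possible. It would still leave controls without a matching date and the primary endpoint dependent on recall.

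A third is that the power loss rests on rates nobody has stated. That is right. The figures in step 5 show sensitivity only, and a reader should not infer that the study is underpowered.

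What the replies leave untouched is the missing completion measurement, which does not depend on the calendar, and the undefined time origin, which is what makes the calendar question unanswerable.

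**Conclusion.** The concern holds in two parts of different strength.

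- **Settled by the text:** completion is a primary time and the basis of the power rates, yet none of the three collection points measures it, and controls have no completion date. The follow-up clock starts at an undated enrolment that precedes randomisation.
- **Strong but conditional:** month 12 precedes completion on 79–100% of January–May enrolment days for starts between 1 August and 15 September. Within April–May the range is 49–100%. It does not precede completion if the programme starts within 3 months of month 0, as under a summer randomisation clock.

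A weak 12-month result could reflect timing; the documents do not allow the firmer statement that it would. Nor do they support a reading that the 18-month comparison fails for the treated arm: under every start examined with January–May enrolment, that visit falls 0.5–7.0 months after programme end. This is a point to correct, not one that invalidates the trial.

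**What to change.** 1. Define month 0 as the cohort's programme start date, the same calendar date in both arms.
2. Name one primary time that falls after programme end and before the next intake. Either ask one employment question of both arms at the end of the programme year, which matches the powered rate, or use month 12 with the visit completed before any wait-list control starts PS+ASD. The second option has no spare time: with one intake per school year (assumed), month 12 from programme start is the next intake date.
3. If no end-of-programme question is added, remove completion from the primary endpoint.
4. Treat month 18 as follow-up and report by arm how many controls have started the programme. On the new clock, a control who joined the next intake would be about 18 − 12 = 6 months into it.
5. If data are already collected (Background, Rationale and Goals, item 6, already describes results without naming a time), report months from programme end at each visit and label any 12-month result taken before programme end as in-programme.

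**Cost.** The end-of-programme question is one short call per participant. Moving the clock instead delays visits by the gap from enrolment to start, about 3–8 months for January–May enrolment and a 1 September start, with somewhat more loss to follow-up in families who relocate often. The month-18 comparison may include exposed controls. Step 5 needs only dates and no new contact with participants.
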